### *6.6 Key Exclusion Criteria*

1). Under 18 years of age; 2) does not have regular, daily access to a smartphone 3) unable to communicate fluently in English (as the current Cobalt assessments and resources are in English at this

## Effect of a Digital Engagement Strategy on Healthcare Worker Mental Health and Well-being: A Randomized Controlled Trial

time), 4) does not work at least 4 hours per week in either a hospital or outpatient based setting, 5). Not willing to sign the informed consent document.

### 7. Subject Recruitment

#### 7.1 Target Population

The population of interest for this proposal is HCWs who in the midst of COVID-19 are at increased risk for mental health symptoms and conditions. We will also utilize University groups and motivated mental healthcare champions to specifically promote inclusion of female and underrepresented minority HCW in the RCT and qualitative aim. This focus aligns with the RFA which identifies vulnerable populations as: medical personnel with direct patient care and NIH-designated health disparity racial/ ethnic minorities. We specifically include a broad definition of HCWs (e.g. physicians, nurses, certified nursing assistants, lab technicians, radiology technicians, physical therapists, occupational therapists, pharmacists, pharmacy technicians, patient registration staff, coroners, receptionists/patient intake coordinators, environmental service personnel) that are not routinely evaluated jointly and with the same intervention. While much of the attention in the pandemic has been on physicians and nurses we aim to focus on a broader group that is at risk for COVID-19 and mental health symptoms and conditions. Our study samples demographic information, specifically gender, race, and ethnicity compared to the larger employee group. We will receive de-identified proportions of this information from University of Pennsylvania administration. Demographic information will include: % female, % male, % non-reported/missing, % American Indian/Alaskan Native, % Asian, % Black or African American, % Native Hawaiian/Pacific Islander, % White, % I do not wish to answer, % non-reported/ missing, % Hispanic / Latinx, and % non-reported/missing. The demographic information would be used for internal discussions only with the Penn Medicine research personnel listed on our IRB HSERA protocol (IRB #: 848844).

#### 7.2 Subjects at Penn 1,275

#### 7.3 Accrual

To recruit potential study participants, we will send an email about the study to the entire Penn Medicine employee listserv, as these individuals are the same recipients of Penn Medicine news and Covid-19 updates who have received prior information about the availability of Cobalt. Emails will be sent up to 5 times to this employee list. The plan to outreach to employees in this manner has been approved by both Penn Medicine Human Resources and the Penn Medicine Chief Operation Officer. We will specifically engage recruitment champions in the study design and for support in extending the reach of the recruitment email to underrepresented minority HCWs. These recruitment champions will include each Departments Vice Chair for Diversity and Inclusion to support sending the email about the study to their Departments and groups within their Departments specifically focused on diversity and inclusion. We will also engage Centers, Departments, and Groups at Penn Medicine to support dissemination of the study announcement. These include the Office of Inclusion and Diversity, the Alliance of Minority Physicians, Penn Medicine Center for Health Equity Advancement, Bold Solutions Initiative, FOCUS on health and leadership for women, Penn Promotes research on sex and gender in health, and the Program for Health Equity in Education and Research. Furthermore, we will recruit in-person across the Penn Medicine campus such as tabling outside of prominent buildings and departments (New Pavilion and cafeterias) and attend department morning huddles / meetings to accommodate staff members who have limited access to their email accounts. We will also be intentional about diversity of representation in the images in all study materials and highlight the diversity in our project team. We base our power considerations on baseline data presented in an RCT conducted by Graham et al. In their study, they report a mean baseline PHQ-9 of 14.0 (SE=5.0) and mean GAD-7 of 11.6 (SE=4.6). We assume a type I error rate of 2.5% (.05/2) to account for the two

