## Effect of a Digital Engagement Strategy on Healthcare Worker Mental Health and Well-being: A Randomized Controlled Trial

Initiative, FOCUS on health and leadership for women, Penn Promotes research on sex and gender in health, and the Program for Health Equity in Education and Research. Furthermore, we will recruit in-person across the Penn Medicine campus such as tabling outside of prominent buildings and departments (New Pavilion and cafeterias) and attend department morning huddles / meetings to accommodate staff members who have limited access to their email accounts. We will also be intentional about diversity of representation in the images in all study materials and highlight the diversity in our project team. We base our power considerations on baseline data presented in an RCT conducted by Graham et al. In their study, they report a mean baseline PHQ-9 of 14.0 (SE=5.0) and mean GAD-7 of 11.6 (SE=4.6). We assume a type I error rate of 2.5% (.05/2) to account for the two separate outcomes that we will be evaluating. We aim to enroll 1250 participants with the anticipation that there will be 20% attrition.

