### 4. Primary Outcome Variable

Measures were selected based on clinical relevance, validity in the HCW population, and meaningfulness to the target population. To facilitate data sharing, measures below were also identified to align with the NIMH data archive when possible. The primary outcome will be depression and anxiety as measured by the Patient Health Questionnaire (PHQ-9) and General Anxiety Disorder (GAD-7) respectively. PHQ-9 and GAD-7 have been validated and used in multiple studies and provide easy, simple scales to quickly assess for depression and anxiety. PHQ9 is a 9-item score which ranges from 0 (least depressed) to 27 (most depressed). GAD-7 is a 7-item scale which assess the frequency of anxiety symptoms over the past two weeks on a 4-point Likert-scale ranging from 0 (never) to 3 (nearly every day). The total score of GAD-7 ranged from 0 to 21, with increasing scores indicating more severe functional impairments as a result of anxiety.

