## Effect of a Digital Engagement Strategy on Healthcare Worker Mental Health and Well-being: A Randomized Controlled Trial

separate outcomes that we will be evaluating. We aim to enroll 1275 participants with the anticipation that there will be 27.5% attrition.

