
### **9. Analysis Plan**

We will conduct an intent to treat (ITT) analysis. The ITT analysis will include all randomized participants in the groups to which they were randomly assigned. Baseline demographic and clinical characteristics will be reported as frequency and percent for categorical variables and median and distribution for continuous variables. We will compare baseline characteristics between intervention and control arms using t-tests for continuous variables and chi-squared tests for categorical variables. The goal of these comparisons will be to determine if the two arms are balanced on baseline variables after randomization. Our primary analysis will focus on the difference in PHQ-9 and GAD-7 scores at 6 months between the two arms. We will estimate and test differences in means between arms using two- sample

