## Effect of a Digital Engagement Strategy on Healthcare Worker Mental Health and Well-being: A Randomized Controlled Trial

t-tests and generalized linear models that account for baseline measurements of PHQ-9 and GAD-7. Missing data will be assessed for patterns and multiple imputation will be used if deemed appropriate. Baseline covariates that are found to be imbalanced between arms may be adjusted for in the model if they were deemed to be potential confounders a priori to adjust for potential confounding and for efficiency gain. We will use all available PHQ-9 and GAD-7 scores on eligible patients from randomization through the last observation. A p<0.05 will be deemed statistically significant but emphasis will be placed on point estimates and confidence intervals. Secondary outcomes of mental healthcare utilization, satisfaction with connection to services, and qualitative feedback on mobile engagement will also be modeled using GEE with mean models specified based on the distribution of the specific outcome (e.g. Poisson or negative binomial for number of mental healthcare visits, logit for binary responses). Potential associations between system-level or regional level case burden and PHQ-9 and GAD-7 scores at baseline and over-time will be assessed with generalized linear models and GEE. Exploratory Aim 1: Statistical approach: The statistical approach for studying HTE will be to test for the statistical interaction between the intervention and race and separately by gender in the GEE models described above. Although our study was not designed specifically to detect HTE, if 20% of our trial participants are Black (based on targeted recruitment efforts), our study will achieve 80% power (assuming type I error of 0.05) to detect a 1.8 difference in mean GAD-7 scores and a 2.0 difference in mean PHQ-9 scores between arms at 6 months. We anticipate that at least 50% of participants will be female. Hence, our study is powered to detect a 1.2 difference in mean GAD-7 scores and a 1.3 difference in mean PHQ-9 scores between arms at 6 months among women. Aim 2: Power: no power calculation will be performed for this qualitative aim consistent with prior qualitative aims we will aim to interview 80 participants from Aim 1 and evaluate themes until saturation Analysis: Using thematic analysis, we will analyze HCW interview transcripts to identify recurring themes in attitudes and beliefs toward mental health, well-being, and mental health care or resources. Interview audio will be transcribed and uploaded into Nvivo software (available as a Penn resource). In total we plan for up to 80 semi-structured interviews, or until inductive thematic saturation is reached in each group meaning no new themes are emerging. Analysis of qualitative, semi-structured interviews utilizes a series of systematic steps in transcribing, developing a code for thematic content, and subsequent coding of interviews. A modified grounded theory approach will be used to evaluate interview transcriptions. Analysis will begin shortly after the first few interviews are completed. An emergent, iterative open coding process will be followed and two trained coders from the research team will jointly read five transcripts and draft the outline of a codebook. Each coder will then independently code five more transcripts and adjust the codebook as needed. We will review the codes, resolve discrepancies and finalize coding procedures. Following adjudication of any areas of discrepancy, the research team coders will be assigned batches of transcripts for independent coding, sharing 25% of the transcripts in each batch for ongoing inter-rater agreement assessment. We will review coding for interrater reliability, measured by Cohens kappa (0.8), and overall comprehensiveness. If a high kappa is not achieved, further double coding and refining of the code will continue. This approach to coding and analyzing qualitative data has been widely used. Strategies used to ensure reliability and validity in the qualitative data will include a comprehensive audit trail, checks between coders, team debriefing, and corroboration of findings across participants.

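### The trial is sized at 2.5% per primary outcome but significance is declared at p<0.05 unadjusted; a Holm rule in Section 9 would restore 5% familywise control with more power than a fixed split.

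*Combined protocol and SAP*

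**What the plan says.** All references are to the Final Study Protocol unless stated.

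- Section 4 makes both scales primary: "The primary outcome will be depression and anxiety as measured by the Patient Health Questionnaire (PHQ-9) and General Anxiety Disorder (GAD-7) respectively".
- Section 7.3 gives the error rate used for planning: "We assume a type I error rate of 2.5% (.05/2) to account for the two" "separate outcomes that we will be evaluating". The same assumption stands in Section 6.3 of the protocol printed before it in the file.
- Section 7.3 also gives the size: "We aim to enroll 1275 participants with the anticipation that there will be 27.5% attrition".
- Section 9 defines the comparison: "Our primary analysis will focus on the difference in PHQ-9 and GAD-7 scores at 6 months between the two arms".
- Section 9 then gives the only written decision rule: "A p<0.05 will be deemed statistically significant but emphasis will be placed on point estimates and confidence intervals".

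Section 9 names no multiplicity procedure and does not say whether success means one outcome or both. No target difference or power is given for the primary outcomes. The only stated power, in the subgroup text of Section 9, uses a type I error of 0.05.

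**The concern.** Two sections give different error rates for the same pair of tests. Section 7.3 shows that the sponsor meant to allow for two primary outcomes. Section 9, which the analyst will follow, makes no such allowance. If p<0.05 is applied to each scale, the chance of at least one false claim exceeds the 5% that Section 7.3 budgets for.

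The obvious repair, copying 2.5% into Section 9, has a cost of its own. A fixed split holds each outcome to 0.025 whatever the other shows. A second outcome with p between 0.025 and 0.05 would be called non-significant beside a clear result on the first, although 5% familywise control does not require it. Because the sponsor must choose a rule anyway to reconcile the sections, the choice matters now.

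**Working it through.** **Inputs from the documents.** Planning alpha 0.05/2 = 0.025 (Section 7.3); decision threshold 0.05 (Section 9); 1275 enrolled with 27.5% attrition, so 1275 × 0.725 = 924 completers, about 462 per arm; spreads of 5.0 (PHQ-9) and 4.6 (GAD-7), which Section 7.3 labels SE but which work only as SDs.

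**Assumptions.** 1:1 allocation, two-sided tests, normal approximation. The correlation r between the two test statistics is not given, so it is varied from 0 to 0.9.

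**Reproducing the plan.** The 1275 cannot be reproduced, because no primary difference or power is stated. The inputs can be checked on the figures for women (50% of completers, about 231 per arm), at alpha 0.05 and 80% power:

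- GAD-7: (1.960 + 0.842) × 4.6 × √(2/231.1) = 1.20; stated 1.2.
- PHQ-9: (1.960 + 0.842) × 5.0 × √(2/231.1) = 1.30; stated 1.3.

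This supports reading 5.0 and 4.6 as SDs. The figures for Black participants (1.8 and 2.0) match 1250 × 0.80 = 1000 completers, the size in the protocol printed first (1.82 and 1.98), rather than 924 (1.90 and 2.06).

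**Step 1: familywise error if p<0.05 is applied to both.** At r = 0 it is 1 − 0.95² = 9.75%. In general it is 1 − P(|Z1| < 1.960 and |Z2| < 1.960), with Z1 and Z2 standard bivariate normal; see the table. With 2.241 in place of 1.960 (the split), it is 1 − 0.975² = 4.94% at r = 0 and lower for larger r. Holm has the same value when both nulls are true, since its first step is the same test.

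**Step 2: reference effect.** Take true effects that give each outcome 80% power under the split: a standardized effect of 2.241 + 0.842 = 3.083. In points, 3.083 × 5.0 × √(2/462.2) = 1.01 (PHQ-9) and 3.083 × 4.6 × √(2/462.2) = 0.93 (GAD-7).

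**Step 3: compare the rules.** The split claims both outcomes if both p<0.025. Holm claims both if both p<0.05 and at least one p<0.025. These are bivariate normal probabilities with mean 3.083 for each statistic.

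| r | Familywise error, both at 0.05 | Familywise error, split or Holm | Per-outcome power, split → Holm | Power for both, split → Holm | Power for both, each at 0.05 | Power for at least one, split and Holm |
|---|---|---|---|---|---|---|
| 0 | 9.75% | 4.9% | 80% → 85.5% | 64.0% → 75.1% | 75.6% | 96.0% |
| 0.5 | 9.1% | 4.6% | 80% → 84.6% | 68.7% → 77.8% | 78.6% | 91.3% |
| 0.7 | 8.3% | 4.3% | 80% → 84.1% | 71.3% → 79.4% | 80.4% | 88.7% |
| 0.9 | 7.0% | 3.6% | 80% → 83.2% | 75.0% → 81.5% | 83.1% | 85.0% |

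The rise in power for both is also the share of trials in which Holm changes a decision: 75.1 − 64.0 = 11.1% at r = 0, down to 81.5 − 75.0 = 6.5% at r = 0.9.

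**Step 4: sensitivity.** If each outcome has 50% power under the split, power for both goes from 25.0% to 36.1% (r = 0) and from 42.9% to 51.5% (r = 0.9). At 90% it goes from 81.0% to 88.4% and from 86.9% to 91.1%. If only PHQ-9 responds, with 80% power, Holm adds at most 0.2 points to PHQ-9 power.

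**The case against.** The strongest reply is that the plan contains no fixed-split test to improve on. A reader might infer from Section 7.3 that the trial as written throws power away by testing each scale at 2.5%. The documents do not support that: the 2.5% belongs to the power considerations, and the only written rule is p<0.05. Against that rule Holm is stricter and recovers nothing. This stands. The gain from Holm counts only against the split, which becomes the decision rule if the sponsor resolves the conflict by carrying 2.5% into Section 9.

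It is also fair to say that the gain is conditional. Even with real effects on both scales, Holm changes a decision in only about 6% to 11% of trials, and less often as the correlation rises. The larger gain is for winning on both outcomes, and the plan does not define success that way. If it did, the efficient rule would be to test each at 0.05, which is slightly more powerful than Holm for that claim (75.6-83.1% against 75.1-81.5%). This also stands, and the fix allows for it.

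Finally, Section 9 puts its emphasis on confidence intervals, and the split has the merit that its tests agree with simultaneous 97.5% intervals. Under Holm, that interval includes zero whenever the second outcome is significant only at the 0.05 step. This is a real cost, but one sentence of reporting handles it. None of these arguments removes the conflict between the two sections.

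**Conclusion.** The point holds as a conflict to be reconciled, with Holm as the better way to do so when a claim on either outcome is allowed. The unadjusted rule in Section 9 gives a familywise error of about 7% to 9.75%, against the 5% that Section 7.3 implies. The fixed split would be valid (3.6% to 4.9% when neither outcome is affected). Compared with it, Holm adds about 3 to 5.5 points of power per outcome and about 6 to 11 points for both. It adds nothing for at least one outcome, and almost nothing if only one responds.

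The power figures rest on an assumed 80% power per outcome under the split and on assumed correlations of 0 to 0.9. The differences of 1.01 and 0.93 points also need 1:1 allocation, 924 completers and SDs taken from another trial's baseline. The direction needs none of this: Holm rejects whatever the split rejects and controls familywise error at 5% under any correlation. It recovers part, not all, of the power of testing each outcome at 0.05. This is a worthwhile improvement; the split itself is not an invalid method.

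**What to change.** First state in Section 9 whether success means at least one primary outcome or both.

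- If a claim on either outcome is allowed, add a sentence to Section 9 saying that PHQ-9 and GAD-7 at 6 months are tested with the Holm procedure at a familywise two-sided 5% level: the smaller p-value is compared with 0.025 and, if significant, the other with 0.05. Limit the general p<0.05 sentence to analyses outside this pair, and have Section 7.3 refer to the rule.
- If both outcomes are required, state that each is tested at 0.05 and remove the split from Section 7.3.

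Under Holm, report adjusted p-values with simultaneous 97.5% intervals. Say that decisions follow the adjusted p-values, since the second interval can include zero when that outcome is declared significant.

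The cost is a few sentences, written before unblinding, with no extra participants or data.

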## Effect of a Digital Engagement Strategy on Healthcare Worker Mental Health and Well-being: A Randomized Controlled Trial

separate outcomes that we will be evaluating. We aim to enroll 1275 participants with the anticipation that there will be 27.5% attrition.

### *7.4 Patient Subject Recruitment*

To recruit potential study participants, we will send an email about the study to the entire Penn Medicine employee listserv, as these individuals are the same recipients of Penn Medicine news and Covid-19 updates who have received prior information about the availability of Cobalt. Emails will be sent up to 5 times to this employee list. The plan to outreach to employees in this manner has been approved by both Penn Medicine Human Resources and the Penn Medicine Chief Operation Officer (see letters of support). Exploratory Aim1 specifically seeks to determine if the effect of the intervention varies across patient subgroups (e.g. race and gender) as we recognize the importance of evaluating the effect of Cobalt in these specific populations. We will specifically engage recruitment champions in the study design and for support in extending the reach of the recruitment email to underrepresented minority HCWs. These recruitment champions will include each Departments Vice Chair for Diversity and Inclusion to support sending the email about the study to their Departments and groups within their Departments specifically focused on diversity and inclusion. We will also engage Centers, Departments, and Groups at Penn Medicine to support dissemination of the study announcement. These include the Office of Inclusion and Diversity, the Alliance of Minority Physicians, Penn Medicine Center for Health Equity Advancement, Bold Solutions Initiative, FOCUS on health and leadership for women, Penn Promotes research on sex and gender in health, and the Program for Health Equity in Education and Research. Furthermore, we will recruit in-person across the Penn Medicine campus such as tabling outside of prominent buildings and departments (New Pavilion and cafeterias) and attend department morning huddles / meetings to accommodate staff members who have limited access to their email accounts. We will also be intentional about diversity of representation in the images in all study materials and highlight the diversity in our project team. For enrolled study participants, there is no email or text message follow for nudge messages. However, there is one text message or email follow up message (based on the participants communication preference) to complete survey assessments. For example, the message notes: Hi PARTICIPANT\_FIRSTNAME, when you have a chance, please complete this short well-being survey: It only takes about 2 minutes! Thanks for your reply! For 6 and 9 month follow up survey reminders, we will send the following text message or email, Hi PARTICIPANT\_FIRSTNAME, please complete the last follow up survey by clicking here: Once you complete it, \$75 will be loaded on your ClinCard account. To promote retention, participants will be emailed up to 4 times and texted (up to three times) to nudge survey and assessment completion. For compensation, each participant will receive up to \$200: \$50 at enrollment, \$75 at 6 months and \$75 at 9 months for 3 total surveys. Submission for subject reimbursement will occur immediately upon completion of surveys and assessments and occur through the Way to Health platform which facilitates timely payment. Using data from Aim 1, we will use a deviance sampling approach to identify HCW from the top and bottom 25% percentiles of anxiety and depression scales. This deviant selection is intentional to maximize the potential to identify themes unique to high or low levels of mental health strain. Individual scale scoring will not be revealed in order to limit responder bias, increase response rates and avoid attribution bias. We will recruit participants enrolled in Aim 1 (RCT), using a series of e-mails (up to 4 email invitations) and text messages (up to 3 text invitations). We will contact participants to obtain informed consent for the interview to ensure study procedures are described, answer questions and offer a \$50 gift card for their time. The goal is to conduct 80 audio-recorded semi-structured interviews (~20-30 minutes). Interview questions will be aligned with themes from our preliminary studies and focus groups with front line healthcare workers early in the pandemic. Participants will be contacted one month following the end of the Aim 1 study period and consented via
